Metrical structures are built upon integer divisions of some unit, just as musical rhythms are built from notes of different values; when speech adheres to a metrical framework, syllables occur at a regular interval, or some integer multiple of that interval. In contrast, more typical conversational prosody is based on linguistic knowledge, particularly syntactic and prosodic knowledge. We propose a "two-route" model of speech planning, in which this planning can be accomplished in one of two ways: according to either a metrical or a linguistic framework, with the latter used to produce typical, conversational speech. Further, we suggest that aphasia may differentially affect these frameworks, such that PWA are a well-suited population with which to test the two-route claim. Individuals within the population may show deficits to one route, both routes, or neither. People with nonfluent aphasia are expected to be unable to use syntax and prosody to construct a fluent speech plan, while those with fluent aphasia will often be able to do so, resulting in varied performance across individuals with aphasia when attempting to use a linguistic framework to produce conversational prosodic timing. Concerning the metrical route, PWA frequently show unusual difficulty processing rhythm and timing information (Zipse et al., 2014). Individuals with this deficit should be prone to difficulty using a metrical framework to organize their speech. The proposed study will explore this two-route model by (1) evaluating whether PWA show true entrainment when speaking along to speech that adheres to either a metrical or a linguistic framework, indicating that they can make use of the framework to predict what comes next in the

signal (Aim1), and (2) test whether PWA benefit from a unison model with either a metrical or a linguistic framework (Aim 2).

II. Specific Aims

The specific aims of this study are to:

1. ***Determine how timing alignment of sentences spoken along with an auditory model is affected by metrical vs. conversational prosody, for people with aphasia and for typical speakers.*** Participants will attempt to speak in unison to an audio recording of two types of sentences: (1) sentences with regularly occurring stressed syllables (metrical) and (2) sentences spoken with a typical, conversational timing pattern (conversational).

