Prediction: PWA will show varied patterns of performance across these tasks. Successful entrainment with one timing framework will not necessarily be associated with successful entrainment to the other type.
2. ***Determine whether people with aphasia benefit from attempting entrainment when the signal consists of (a) sentences produced with metrical prosody, and (b) sentences produced with conversational prosody.*** In a 2x2 design, sentences with metrical vs. conversational prosody will be produced in repetition vs. in unison with a model. The number of accurate syllables produced will be compared across repetition (imitation) and entrainment (prediction) to evaluate the effect of attempting entrainment.
Prediction: PWAs will vary as to whether they benefit from entrainment to sentences with metrical or conversational prosody. Critically, those who benefit from entrainment with one type of prosody will not necessarily benefit from entrainment with the other type.

III. Subject Selection

One-hundred participants will be recruited for this study, including 40 with aphasia, 40 age-matched controls, and up to 20 controls enrolled for the purposes of piloting and refining stimuli, as well as training study staff on data collection procedures. All participants must be between the ages of 18 and 80 and pass a hearing screening, demonstrating thresholds ≤ 40 dB at 1 kHz, 2 kHz, and 4 kHz in at least one ear, tested in a quiet room. Hearing screens will be conducted by the PI, who is a licensed speech-language pathologist, or by a research assistant trained by the PI, after informed consent has been obtained. Given that the screening thresholds are quite liberal, it is not anticipated that many participants will be excluded from the study based on the hearing criterion.

Control participants must exhibit native-speaker level fluency in American English and must not report any history of speech or language disorders, stroke, or other neurological disease. They must repeat both sentences in the short form of the Sentence Repetition subtest of the Boston Diagnostic Aphasia Examination (BDAE; Goodglass, Kaplan, & Barresi, 2001) without any errors, given a maximum of 2 attempts per sentence. They must also pass the Mini-Cog screening (Borson et al., 2000), a short cognitive screening measure that has been validated in older Americans to have

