Audio files of stimuli and responses produced in the unison conditions will be labeled using a partially automated approach to extract the moment of voicing onset for vowels in target syllables (refer to Fig. 2). First, time intervals surrounding each syllable onset will be hand labeled using Praat Software (Boersma & Weenink, 2016). Second, the Praat autoVOT plugin (Keshet et al., 2014) will be used to efficiently extract the timing of voicing onset (fig. 4). The autoVOT plugin has been demonstrated to perform comparably to manual annotation (Buz et al., 2018) and was judged reliable in an initial sample of our own data.

[figure not shown]

Fig. 4: Example of autoVOT labeling procedure. The blue shaded region indicates the manually labeled search window that is input to the autoVOT program. The red line shows the voice onset moment identified by the autoVOT.

Voice onset moment time points will be used to calculate the timing offset between participant productions and the corresponding time points in the stimuli. The line delay documented at the beginning of each participant's experimental session will be subtracted from each extracted timepoint from participant productions, and the stimulus timepoint will then be subtracted from that difference, calculated as

$$(p - d) - s$$

where p represents participant voice onset moment, d represents line delay, and s represents stimulus voice onset moment. The resulting value represents whether and how far productions occur before or after a stimulus.

For statistical analysis, separate mixed-effects linear models will be run for controls and PWAs, with signed timing offset for each target syllable as the outcome.

Aim 2: Determine whether people with aphasia benefit from attempting entrainment when the signal consists of (a) sentences produced with metrical prosody, and (b) sentences produced with conversational prosody.

All sentences used to address Aim 2 will be transcribed and scored for syllable-level accuracy, according to a previously established, comprehensive set of rules (Kershenbaum et al., 2017). Twenty percent of utterances, distributed across PWA, will be independently transcribed and scored by a second rater to evaluate inter-rater reliability.

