A 2x2 ANOVA will be used to evaluate the relative benefit of entrainment on % of syllables correct for speech with conversational vs. metrical prosody. Exploratory follow-up correlations will evaluate any possible relationship between a “metrical benefit” and other participant

characteristics including fluency (from the picture description task), AOS severity, and entrainment ability (from the tap to a metronome, entrain a syllable to a metronome, and tap to music tasks).

Power Analysis

Aim 1: The data from this study will be used to establish effect sizes to enable a meaningful power analysis in an external grant application; there are currently no studies of which we are aware comparing time-locked measures of speech entrainment across PWA and controls. To try to ensure that the study is adequately powered, even if some of the PWA are unable to produce all of the target words/syllables or if the target landmarks are not identifiable, we have included a rather large number of target landmarks (4-16 labeled landmarks per stimulus, and 8 stimuli/condition, yielding ~80 data points/condition for each participant).

Aim 2: Based on previous work from our group (Kershenbaum et al., 2017), the effect size of attempted speech entrainment is 0.975 (Cohen's d). This is based on % of accurate syllables produced by PWA, compared across 2 conditions: attempting to entrain to spoken sentences versus repeating them solo. In that study, the spoken stimuli were metrical, with regular, predictable timing. We anticipate that sentences with conversational prosody may result in less of an entrainment gain for many PWA. Therefore, we used 0.7 as an estimated effect size, an alpha level of 0.05, and 0.90 for power. With these constraints, the needed sample size is 19 PWA (sample size analysis conducted with G*Power; Faul et al., 2007). Our proposed sample size of 25 allows for some participant attrition, data loss, or unscorable data (e.g., PWA who cannot produce enough scorable tokens).

VII. Risks and Discomforts

For people with aphasia, there is a risk that the experimental tasks may be difficult and frustrating to complete.

There is also a risk that participant privacy could be compromised in some way. Study data, including audio recordings of participants and calculated results will be maintained on encrypted Partners computers. Any paper records will be kept in a file drawer in a locked office at the MGH Institute.

VIII. Potential Benefits

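### Aim 1 predicts that metrical and conversational entrainment can come apart within a person, but its only analysis, a per-group model of signed timing offset, contains nothing that estimates this

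*Combined protocol and SAP*

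**What the plan says.** The combined protocol and SAP states the Aim 1 prediction in two sentences (II. Specific Aims). The first is "PWA will show varied patterns of performance across these tasks". The second is "Successful entrainment with one timing framework will not necessarily be associated with successful entrainment to the other type". Both concern individuals. The rationale in I. Background and Significance does too: "Individuals within the population may show deficits to one route, both routes, or neither".

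The heading of Aim 1 asks something different, a question about averages: "Determine how timing alignment of sentences spoken along with an auditory model is affected by metrical vs. conversational prosody".

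The whole statistical analysis for Aim 1 (VI. Biostatistical Analysis) is one sentence: "separate mixed-effects linear models will be run for controls and PWAs, with signed timing offset for each target syllable as the outcome". It names no fixed effect, not even prosody, and no random effect for participant or sentence. The only correlations in the plan are exploratory and belong to Aim 2. They relate a metrical benefit to fluency, apraxia severity and musical or metronome entrainment, not metrical to conversational timing.

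Aim 1 has no power calculation. The Power Analysis relies on the volume of repeated measures: "4-16 labeled landmarks per stimulus, and 8 stimuli/condition, yielding ~80 data points/condition for each participant".

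**The concern.** The prediction is about how two abilities go together across people. To test it, the plan needs (a) a measure of how well each participant aligns in each prosody and (b) an estimate of how those two measures are associated. Neither is planned, and no rule says when a participant's entrainment counts as successful.

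The outcome adds a second difficulty. Signed offset is positive when the speaker is late and negative when early. Averaged over syllables it shows a consistent lead or lag, but a mean near zero can come from tight alignment or from wide scatter on both sides.

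At stake is the central claim of the study, the two-route model. Aim 1 could finish with a clear mean timing difference, or with none, and the prediction would be no better or worse supported than before.

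**Working it through.** **Inputs from the document.** 8 stimuli per condition and 4–16 landmarks each (VI, Power Analysis). Number of PWA: 40 in III. Subject Selection ("including 40 with aphasia, 40 age-matched controls"), 25 in the Power Analysis ("Our proposed sample size of 25 allows for some participant attrition, data loss, or unscorable data"). No Aim 1 variance components are given, so every SD below is an assumption.

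**Step 1: the plan's own figure.** The midpoint of 4 and 16 is 10, and 10 × 8 = 80 points per condition. The stated figure reproduces (range 4 × 8 = 32 to 16 × 8 = 128).

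**Step 2: the mean effect carries no information on the association.** Let each participant's true metrical and conversational offsets have between-participant SD 60 ms (assumed) and correlation ρ. The mean difference does not depend on ρ. Ignoring landmark noise, its standard error is √[2 × 60² × (1 − ρ)/n]. With n = 40:
- ρ = −0.5: √(10,800/40) = 16.4 ms
- ρ = 0.9: √(720/40) = 4.2 ms

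Only the precision changes. No value of the estimated mean effect distinguishes abilities that are opposed from abilities that are nearly identical.

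**Step 3: signed offset does not measure success.** A participant with equal numbers of offsets +a and −a has mean signed offset 0 for every a, while the mean absolute offset is a. Correlating participants' mean signed offsets would show whether habitual leaders or laggers stay so in both prosodies, not whether they align well in both.

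**Step 4: how precisely the association could be known.** By Fisher's z, the 95% limits are tanh[arctanh(r) ± 1.96/√(n − 3)].

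| PWA | 1.96/√(n − 3) | r = 0 | r = 0.5 |
|---|---|---|---|
| 40 | 0.322 | −0.31 to 0.31 | 0.22 to 0.70 |
| 25 | 0.418 | −0.40 to 0.40 | 0.13 to 0.75 |

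These limits ignore measurement error in each participant's score.

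**Step 5: a conditional check on the prosody test.** Suppose the model were fitted with participant intercepts only. Let τ be the SD of the participant-specific prosody difference, ω the speaker-by-sentence SD, and σ = 100 ms the landmark SD, with 8 sentences and 80 points per condition. Per participant, the true variance of the contrast is τ² + 2(ω²/8 + σ²/80). The model uses about 2(σ² + ω² + τ²/4)/80. With k the square root of their ratio, the rejection rate under no mean effect is 2[1 − Φ(1.96/k)].

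| τ (ms) | ω (ms) | true / model variance | k | rejection at nominal 5% |
|---|---|---|---|---|
| 0 | 0 | 250 / 250 | 1.00 | 5% |
| 20 | 0 | 650 / 252.5 | 1.60 | 22% |
| 0 | 30 | 475 / 272.5 | 1.32 | 14% |
| 0 | 50 | 875 / 312.5 | 1.67 | 24% |
| 20 | 30 | 875 / 275 | 1.78 | 27% |
| 50 | 50 | 3375 / 328.1 | 3.21 | 54% |

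Simulation agrees. The ratio does not involve the number of participants, so 40 instead of 25 PWA does not help. Rows three and four show that part of the inflation arises with no participant-by-prosody variation at all.

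**Step 6: a participant slope alone is not a full repair.** A test on participant-level differences holds 5% in these settings. But paired sentences share target words and are still different sentences (V. Study Procedures, Experimental Stimuli). A sentence SD of 10–20 ms (assumed) adds 2 × 10²/8 = 25 to 2 × 20²/8 = 100 ms² to the variance of the contrast, and more participants do not reduce it. With τ = 20, ω = 30 and n = 40, the participant-level variance is 875/40 = 21.9. The true total is then 46.9 to 121.9, and the participant-level test rejects about 17–40% of the time if the conclusion is meant to reach beyond these sentences. With τ = 50 it is about 9–19%.

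**The case against.** The strongest reply is that the plan does not say what a critic might read into it. A reader might infer that Aim 1 will be tested with an intercept-only model and therefore has a false-positive rate of 27–54%. The documents do not support that. The random effects are unspecified, a participant-by-prosody term is not excluded, and all the SDs in Step 5 are assumed. Aim 1 also has no stated alpha or formal test: the 0.05 in the Power Analysis belongs to Aim 2, and the Aim 1 data are described as a source of effect sizes for later work. This part of the reply stands, so the rejection rates are only a reason to write the terms down.

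It is also fair to say that a mean prosody contrast on signed offset answers the heading of Aim 1. Lead and lag matter in their own right, because the Background distinguishes prediction from close shadowing. That stands too, and the signed-offset analysis should stay. It still does not address the prediction.

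Finally, the prediction is weakly worded: a statement that success need not be associated is hard to contradict, and r = 0.5 could be read either way. That is a reason to report an estimate with its interval instead of a pass/fail test.

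**Conclusion.** The gap is real and does not depend on any assumed variance. Aim 1 makes a person-level prediction and plans only a group-level analysis of an outcome in which early and late errors cancel. Nothing elsewhere in the document supplies the missing association or a participant-level measure of success.

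The error-rate issue is secondary and conditional: about 22% at nominal 5% with a prosody-slope SD of 20 ms, landmark SD of 100 ms, 80 points per condition and no speaker-by-sentence variance, and about 27–54% with a speaker-by-sentence SD of 30–50 ms and a slope SD of 20–50 ms. It vanishes if both of these SDs are zero, although the predicted variation between PWA makes a zero slope SD unlikely.

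A reader might also infer that adding a random prosody slope to the signed-offset model would be enough. It would not: the correlation would describe habitual lead or lag, and sentence-by-prosody variation would remain unmodelled.

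**What to change.** In VI. Biostatistical Analysis, Aim 1, keep the signed-offset model for the mean prosody question, state its terms, and add the following:

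1. **Alignment measure.** Define alignment per participant and prosody so that early and late errors do not cancel, for example mean absolute offset or within-person SD of the offset. Say which is primary. The SD ignores a constant lag, so it would score steady shadowing as good alignment; the absolute offset would not.
2. **Model, per group.** A prosody fixed effect; two correlated participant effects, one per prosody; and sentence-level effects that include pair-by-prosody variation. A speaker-by-sentence term is also advisable. Without it, a speaker-by-sentence SD of 30 ms alone adds 2 × 30²/8 = 225 ms² to the apparent variance of the participant-specific prosody effect, an SD of 15 ms. Absolute offsets are skewed, so state any transformation.
3. **Assessment of the prediction.** Report the between-participant SD of the prosody effect and the metrical-conversational correlation with a 95% confidence interval, named as the assessment of the Aim 1 prediction.
4. **Description.** Cross-tabulate PWA as inside or outside the control range in each prosody.

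The cost is wording and analysis time, with no new data. The interval for the mean prosody effect will be wider than one from intercepts only. The correlation will be imprecise, about ±0.31 at r = 0 with 40 PWA or ±0.40 with 25, so the two sample sizes in the document should be reconciled. With 8 sentences per condition the sentence-level variances will be poorly estimated, so the plan should state a fallback if the model does not converge.

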In considering why and how unison speech improves fluency, an important question is how the participant's production is temporally related to the model. In unison speech, the speaker knows the target utterances ahead of time (e.g., through memorization, repetition, or having the printed text) and can therefore align their productions very closely with the model, with mean between-speaker asynchronies as low as 40-50 ms in some conditions. When two speakers attempt to speak synchronously (as opposed to one speaker aligning with a recording), there is an alternation between who "leads" in time (Cummins, 2003). Taken together, the very short between-speaker asynchronies and lack of a consistent "leader" suggest that speaking in synchrony is an active process, collaborative when it involves two active speakers, and entails prediction of what is coming next in the signal. It is *not* the case that one speaker is closely shadowing the other. Neurotypical speakers are able to generate precise speech timing predictions from their knowledge as fluent speakers of the language in question, a limited amount of data on how the conversation partner speaks, and an understanding of a shared goal, and use those predictions to guide their speaking, a complex motor action. This is *entrainment*: aligning a motor action with an external signal.

None of the existing studies examining unison speaking in PWA have reported asynchronies between the participants' productions and the model. Indeed, it seems that few, if any, of these studies time-locked the recording of participants' productions to the stimulus. It therefore remains unknown whether PWA truly entrain their speech during unison productions, under what conditions they are able to do so, how this varies across individuals with aphasia, and whether true entrainment is needed in order for a unison benefit to be conferred.

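### Aim 1's only named outcome, signed timing offset, tests mean lead or lag; with near-equal mean lags and balanced errors it has almost no power for a prosody difference in closeness or consistency, and no other planned analysis tests this (cheap improvement)

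*Combined protocol and SAP*

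**What the plan says.** Section II, Aim 1 asks how "timing alignment of sentences spoken along with an auditory model is affected by metrical vs. conversational prosody", in PWA and in typical speakers. Section I puts the purpose as "evaluating whether PWA show true entrainment when speaking along to speech that adheres to either a metrical or a linguistic framework".

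Section VI, Aim 1 defines the offset as (p - d) - s: participant voice onset, less line delay, less stimulus voice onset. It explains that "The resulting value represents whether and how far productions occur before or after a stimulus". The analysis is one linear mixed model per group, "with signed timing offset for each target syllable as the outcome". Fixed effects, random effects and residual structure are not listed; the metrical-versus-conversational contrast is inferred from the aim.

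The rest of Section VI is a 2x2 ANOVA on percentage of syllables correct and exploratory correlations of a metrical benefit with participant characteristics. Neither compares the size or spread of sentence asynchronies between prosody types.

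Section I rests its account of entrainment on two features together, "the very short between-speaker asynchronies and lack of a consistent" leader, and reports synchronous speech "with mean between-speaker asynchronies as low as 40-50 ms in some conditions".

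The Aim 1 power paragraph gives no effect size or SD. It says "The data from this study will be used to establish effect sizes to enable a meaningful power analysis in an external grant application" and describes the data as "4-16 labeled landmarks per stimulus, and 8 stimuli/condition, yielding ~80 data points/condition for each participant".

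**The concern.** A contrast of signed means answers whether productions run earlier or later under one prosody than the other. It does not measure how tightly they follow the model. A mean offset near zero can come from close synchrony, or from erratic productions whose early and late errors cancel. Section I treats short asynchronies as part of the evidence for entrainment, so closeness belongs to the question Aim 1 asks.

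Suppose PWA follow both sentence types with the same average lag but less steadily on one, with errors balanced around that lag. The named outcome would then show no prosody effect, and the effect size carried into the later grant application would be near zero. A spread measure could still be computed afterwards from the same time points, but it would be post hoc.

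**Working it through.** **Plan's own figure.** Eight stimuli per condition, with the midpoint of 4 and 16 landmarks: 8 x 10 = 80. The stated figure of about 80 reproduces (range 8 x 4 = 32 to 8 x 16 = 128).

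**Inputs.** From the plan: 8 stimuli, 4 to 16 landmarks, and either 40 PWA (Section III) or 25 PWA (Section VI, power for Aim 2). Both numbers are used because the sections differ. Assumed, because the documents give none: landmarks per sentence 4, 6, 8, 10, 10, 12, 14, 16; between-person lag SD 40 ms; person-by-condition lag SD 20 ms; sentence-lag SD 30 ms; person-specific jitter with log-SD 0.3 shared and 0.3 by condition.

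**Signed contrast by hand.** When mean lags are equal, the expected condition difference is 0 whatever the jitter. The rejection rate is therefore the 5% error rate at any number of participants or landmarks. When lags differ by 20 ms with jitter 60 ms, the variance of a participant's paired difference is 2 x 20² + 2 x 30² x (912/80²) + 2 x 60²/80 = 800 + 256.5 + 90 = 1146.5, where 912 is the sum of squared landmark counts. The SD is 33.9 ms and the standardised difference 20/33.9 = 0.59. Two-sided paired-t power is 81% for 25 and 95% for 40, in line with the simulated 79% and 94%.

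**Absolute offset by hand.** For a normal offset with mean m and SD s, E|x| = s√(2/π)·exp(-m²/2s²) + m[1 - 2Φ(-m/s)]. Using jitter alone, going from s = 60 to s = 120:

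- m = 0: 47.9 to 95.7 ms, a difference of 47.8
- m = 100: 102.4 to 127.2 ms, a difference of 24.8
- m = 150: 150.2 to 162.1 ms, a difference of 11.9

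Absolute offset thus loses sensitivity to spread as the lag moves away from zero.

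**Simulation.** Rejection at 0.05, in percent, 25 PWA / 40 PWA. 2,000 runs per row; paired participant-level t-tests stand in for the mixed-model contrast. Detrended SD is the log within-participant SD after removing each sentence's mean lag and linear drift.

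| Scenario | Signed | Absolute | Unadjusted log SD | Detrended log SD |
|---|---|---|---|---|
| Equal lag 100, jitter 60 vs 120 | 5 / 5 | 97 / 99.9 | 100 / 100 | 100 / 100 |
| Equal lag 150, jitter 60 vs 120 | 6 / 5 | 72 / 90 | 100 / 100 | 100 / 100 |
| Equal lag 100, jitter 60 vs 80 | 5 / 5 | 24 / 38 | 86 / 98 | 88 / 98 |
| 200 ms drift in one condition, mean lag unchanged | 5 / 6 | 34 / 51 | 99.8 / 100 | 5 / 5 |
| Sentence-lag SD 30 vs 90 | 5 / 5 | 59 / 80 | 99.9 / 100 | 6 / 6 |
| Lags 100 vs 120, jitter 60 | 79 / 94 | 69 / 88 | 5 / 4 | 4 / 4 |
| Lags -100 vs +100, jitter 60 | 100 / 100 | 5 / 4 | 5 / 5 | 5 / 5 |

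No single measure covers every row.

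**Sensitivity.**

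- Person-by-condition lag SD 40 ms: signed for 100 vs 120 ms falls to 36 / 54. By hand, the variance is 3200 + 256.5 + 90 = 3546.5, SD 59.6, ratio 0.34. Absolute falls to 81 / 96 in the first row and 44 / 67 in the second.
- By-condition log-SD variation 0.5: detrended SD for 60 vs 80 falls to 48 / 71.
- Half the landmarks missing, 60 vs 80: detrended SD 72 / 91, with about 20 of 25 or 32 of 40 PWA keeping enough landmarks (at least 3 per sentence and 8 residual degrees of freedom per condition, also assumed).
- Abrupt 200 ms mid-sentence step, same jitter: detrended SD rejects in 99 / 100, so a pause still counts as inconsistency.
- Random-intercept-and-slope model on signed offset (100 runs each, some convergence warnings): 9 / 3 in the first row and 84 / 96 for 100 vs 120 ms, broadly as above.

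**The case against.** The strongest reply is that the null result is built in. Impose equal means and symmetric jitter, and a test of means must reject at 5%. Real loss of alignment may well move the mean, and then the signed model sees it. With right-skewed jitter (mostly late errors) of SD 60 versus 80 ms, the signed contrast rejects in about 61 to 66% of runs with 25 PWA and 82 to 83% with 40. With 50 ms of drift from a common onset it rejects in about 94% and 99%. This stands. It is why the point is limited to equal or nearly equal mean lags with roughly balanced errors.

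A second reply is that a detrended SD is itself blind to centred drift and to sentence-to-sentence lag, both of which are losses of alignment. This also stands (about 5% in those rows). Adding that measure alone would not close the gap.

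Third, Section I contrasts prediction with shadowing, and signed offset fits that contrast. Agreed: a reader might infer that signed offset is the wrong outcome or that Aim 1 is invalid, and the documents do not support this.

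A reader might also infer that Aim 1 will report no prosody effect. That goes too far. The model terms are unlisted, so a condition-specific residual variance is neither planned nor excluded, and nothing in the documents shows that mean lags will be equal.

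Finally, Aim 1 is meant to supply effect sizes and has no stated alpha or target effect, so the consequence is modest. That is reflected in the verdict.

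**Conclusion.** The point holds in limited form, as a cheap improvement of modest severity. Signed offset is a sound lead/lag outcome. When mean lags are equal or nearly equal and errors are balanced, it stays at about 5% rejection however large the difference in spread and however many landmarks or participants are added. No other analysis in Section VI fills that gap. When looser alignment also shifts the mean, through late-skewed errors, falling behind from a common onset, or mean lags about 20 ms apart under the assumed SDs, the signed model can detect it.

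Every lag and SD used here is an assumption. How often the blind case would occur in this study cannot be judged from the documents, and confidence in its practical importance is medium.

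**What to change.** In Section VI, keep the signed-offset model as the lead/lag outcome. From the same time points, prespecify these metrical-versus-conversational comparisons in each group, each with an estimate and confidence interval:

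- (a) absolute offset |(p - d) - s|, for overall closeness;
- (b) log within-participant SD of the offset after removing each sentence's mean lag and linear drift, for consistency.

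Report the unadjusted SD beside (b), since (b) alone does not show drift or sentence-to-sentence lag and (a) is weak for spread when lags are far from zero. Do not read the unadjusted SD as steadiness on its own, because it mixes jitter with both of these. Label the additions as secondary to the signed outcome, or apply Holm. State a minimum number of scorable landmarks, set by the team.

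Cost: a few sentences in Section VI, with no new data or labelling. Downsides: extra Aim 1 comparisons; an SD that is unstable or missing for PWA with few scorable landmarks (about 5 of 25 or 8 of 40 lost in the half-missing case); and a spread measure that also takes in landmark-labelling error and mid-sentence pauses.

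This does not supply the unlisted model terms, nor does it test the Section II prediction that success with one framework need not go with success on the other within individuals. Both need separate attention.

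### Aim 2 asks whether unison speech helps with each prosody, but the one named test compares the benefit between prosodies, and the 19-participant power figure belongs to a unison-versus-solo contrast that the analysis section does not name

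*Combined protocol and SAP*

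**What the plan says.** - **Question.** Aim 2, in II. Specific Aims and again in VI. Biostatistical Analysis, asks whether PWA gain from attempting entrainment with (a) metrical and (b) conversational sentences. Specific Aims says that accuracy will be compared between repetition and entrainment. V. Study Procedures, Experimental Task Design, says that each solo condition will be set against its matching unison condition. Neither place names a test.
- **Prediction.** Specific Aims adds that "those who benefit from entrainment with one type of prosody will not necessarily benefit from entrainment with the other type".
- **Analysis.** VI. Biostatistical Analysis, Aim 2, gives a 2x2 ANOVA to "evaluate the relative benefit of entrainment on % of syllables correct for speech with conversational vs. metrical prosody". The only other Aim 2 analysis is a set of correlations labelled exploratory.
- **Power.** Power Analysis, Aim 2, starts from an earlier d of 0.975 for metrical stimuli: "This is based on % of accurate syllables produced by PWA, compared across 2 conditions", namely unison and solo. It then lowers the value, because the authors expect a smaller unison gain for many PWA when the prosody is conversational. The settings for the calculation are given as follows: "Therefore, we used 0.7 as an estimated effect size, an alpha level of 0.05, and 0.90 for power". The result reported from these settings is a need for 19 PWA. The software is named; the test, its sidedness and the standardisation of d are not.
- **Numbers.** The same paragraph continues: "Our proposed sample size of 25 allows for some participant attrition, data loss, or unscorable data". III. Subject Selection plans 100 participants, "including 40 with aphasia, 40 age-matched controls" and up to 20 pilot controls.

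**The concern.** Questions (a) and (b) each concern unison minus solo within one prosody. The ANOVA sentence aims at the difference between those two benefits. That difference can be null when both prosodies help equally or when neither helps. It can be significant when only one helps, or when both help unequally. The production main effect, which the ANOVA also yields, averages over prosody and cannot separate (a) from (b). If the plan stays as written, the choice among main effect, interaction and simple effects is left until after the data are seen.

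The 90% power claim belongs to a unison-versus-solo contrast, so the test that the analysis section describes has no stated power. Because sidedness and type of d are also unstated, the allowance for attrition and unscorable data that justifies 25 PWA cannot be checked.

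**Working it through.** **Inputs.** From Power Analysis, Aim 2: d = 0.7 (planning), d = 0.975 (earlier metrical result), alpha 0.05, power 0.90, stated need 19 PWA, proposed 25. From Subject Selection: 40 PWA.

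**Notation.** Let M and C be unison minus solo % syllables correct for metrical and conversational sentences. Question (a) is mean M, question (b) is mean C, and the ANOVA's relative benefit is mean M − mean C. The main effect is (mean M + mean C)/2.

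**Formula.** For a paired t-test, dz is the mean difference divided by the SD of the differences. The statistic follows a noncentral t distribution with n − 1 degrees of freedom and noncentrality dz·√n.

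**Step 1: reproduce 19.** Take dz = 0.7, one-sided 0.05.
- n = 18: power 0.886.
- n = 19: noncentrality 0.7·√19 = 3.05, critical t 1.734, power 0.901.

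So 19 is reproduced exactly.

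**Step 2: the same effect, two-sided.** A 1-df within-participant ANOVA F is the square of the paired t, so its test is two-sided.

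| n | power, dz = 0.7, two-sided 0.05 |
|---|---|
| 19 | 0.823 |
| 23 | 0.894 |
| 24 | 0.907 |
| 25 | 0.919 |
| 40 | 0.991 |

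The number needed for 90% is 24.

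**Step 3: another route to 19.** If 0.7 is on the raw-score SD, and that SD is equal in the two conditions, then dz = 0.7/√(2(1 − ρ)), with ρ the within-person correlation. Two-sided:
- ρ = 0.60: dz 0.783, n = 20.
- ρ = 0.61: dz 0.793, n = 19.
- ρ = 0.63: dz 0.814, n = 18.

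The result is 19 only for ρ of about 0.605 to 0.627. The documents give no correlation, so this is an assumption.

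**Step 4: margin.**
- At 25 PWA: 25 − 19 = 6 (24%) if 19 are needed; 25 − 24 = 1 (4%) if 24 are needed.
- At 40 PWA: 40 − 24 = 16.

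**Step 5: metrical contrast.** With 0.975 read as dz, two-sided power is 98% at 19 and 99.7% at 25.

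**Step 6: alpha split.** At two-sided 0.025 per contrast, dz = 0.7 needs 28 PWA; power is 86% at 25 and 98% at 40.

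**Step 7: interaction, for scale.** The standardised difference M − C detectable with 90% power, two-sided 0.05, is 0.68 at 25 and 0.53 at 40. The documents give no planning value for it.

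**The case against.** The best defence is that the intended contrasts can be identified by reading the sections together. Experimental Task Design pairs each solo condition with its unison counterpart, Aim 2 is restated with (a) and (b) just above the analysis, and a 2x2 ANOVA can be followed by simple effects. No Aim 2 analysis is called confirmatory, and equating relative benefit with the interaction is a reading, though the natural one. This stands to the extent that the comparisons are planned. What is missing is their statement as tests in the section that governs the analysis.

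Four stronger readings might be inferred, and the documents support none of them:
- *The plan omits the unison-versus-solo comparison.* It does not; Specific Aims and Experimental Task Design both describe it.
- *The powered contrast cannot be identified.* The power paragraph says that it is two conditions, unison and solo. Only sidedness and type of d are open.
- *The sponsor used a one-sided test, or the study is underpowered.* Step 3 shows a two-sided route to 19, and two-sided power at dz = 0.7 is still 92% at 25 and 99% at 40.
- *Naming two group contrasts would test the stated prediction.* That prediction is about which individuals benefit, and group means do not test it.

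It is also fair to say that the earlier result gives a directional expectation. If a one-sided test is meant, the plan should say so.

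**Conclusion.** The point holds as a gap between aim, named test and power statement. The named analysis, taken alone, answers neither (a) nor (b), and the 90% belongs to a contrast that the analysis section does not list. The numerical consequence is modest and conditional. If 0.7 is dz and the test is two-sided, power at 19 is 82% rather than 90%, the need is 24 rather than 19, and the spare margin at 25 is 1 PWA rather than 6. With 40 PWA the margin is ample. If d is on the raw-score SD and the correlation is near 0.61 to 0.62, 19 can stand. The metrical contrast is well covered if 0.975 is dz. The 25-versus-40 mismatch is a separate inconsistency, but it decides which margin applies.

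**What to change.** In VI. Biostatistical Analysis, Aim 2:

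1. Name two within-participant contrasts in PWA as the Aim 2 tests: unison minus solo % syllables correct for metrical sentences, and the same for conversational sentences. Test each two-sided at 0.05, on the stated ground that (a) and (b) are separate questions. If the sponsor prefers to split alpha, use the Step 6 figures.
2. Say that the power calculation applies to these contrasts, with 0.7 as the planning value for the conversational one, and state the type of d. If it is dz, restate the need as 24 PWA. If it is on the raw-score SD, state the correlation assumed.
3. Reconcile 25 PWA with the 40 in Subject Selection, and restate the allowance for attrition and unscorable data against the agreed number.
4. Report the production-by-prosody interaction as an estimate with a 95% CI. Make no 90% power claim for it, and say that a non-significant result will not be read as equal benefit.
5. Do not present the group contrasts as a test of the individual-level prediction.

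The cost is a few sentences and possibly a slightly less favourable stated number or power. The four conditions already supply the data, and no participants are added.
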